# **OTHER TOXICITY**

For any other toxicity, the following principles are recommended:

- Trial treatment can be withheld (breaks of treatment up to 3 months are allowed) until the toxicity resolves and then consider reintroduction.
- In order to avoid unblinding, wherever possible, Investigators should investigate and manage symptoms under the assumption that the participant is receiving 300mg aspirin. However emergency unblinding is available (see section 5.6.1) if it will alter clinical management.
- If the participant is unable to tolerate treatment, contact MRC CTU at UCL to discuss indications and processes for a dose reduction. If a dose reduction is deemed appropriate and the participant is already receiving aspirin 100mg daily or matched placebo, this will result in discontinuation of trial treatment. If receiving aspirin 300mg daily or matched placebo, the lower dose or matched placebo will be supplied.
- Where the trial treatment is withheld for more than a total of 3 months the trial medication should be permanently discontinued.
  - Wherever the trial treatment has been permanently discontinued, follow-up in the trial should continue. Participants who discontinue during the run-in period will be asked for consent to allow passive follow-up data collection using medical records, however no further CRFs will be completed

# TINNITUS

For new episodes of tinnitus of grade 1, aspirin/trial medication can be discontinued for up to 3 months to see if symptoms change or resolve when the trial medication is not being administered, before a definitive decision is made regarding permanent discontinuation of trial medication. Individual cases can be discussed with clinical members of the trial management group by contacting the MRC CTU at UCL.

# **HYPERTENSION**

All participants should have blood pressure assessed prior to registration and throughout participation in the trial, in accordance with the assessment schedules (see flexibility of schedule and follow-up for further information). Patients with a systolic BP $\geq$ 160mmHg or diastolic BP $\geq$ 100mmHg (confirmed on repeated measurement, home monitoring or ambulatory monitoring) prior to registration should have blood pressure treatment optimised before registration.

Patients who are already registered in the trial who have hypertension (BP≥160mmHg or diastolic BP ≥100mmHg), confirmed on repeated measurement, should be referred to their GP for a repeat measurement and blood pressure optimisation where required, or a repeat reading should be taken at home.

If the blood pressure remains elevated (systolic BP $\geq$ 160mmHg or diastolic BP  $\geq$ 100mmHg) on repeated measurement, either at the GP or at home, then please withhold treatment (up to 3

months) until BP is optimised, and notify MRC CTU. An in range reading must be obtained prior to the patient recommencing trial treatment.

### THROMBOCYTOPENIA

If a participant's platelet count falls below  $50 \times 10^9$ /L, the trial treatment should be withheld until it recovers to above this level.

### eGFR

If a participant's eGFR falls below 45ml/min/1.73m^2, please investigate other causes of a deterioration in renal function and consider withholding trial medication until this level improves. Discuss with the MRC CTU for advice.

See Appendix XIV for management of immune related toxicity in POLEM

### 5.4.4 PREGNANCY

Regular use of aspirin may adversely affect a pregnancy and/or foetal development. Regular aspirin use whilst breast feeding can also cause complications in the neonate/infant and should be avoided. Therefore, participants joining Add-Aspirin should not be pregnant or breast feeding at registration and be advised against becoming pregnant during the trial treatment period. If a participant becomes pregnant during the trial, trial treatment should be stopped and a Pregnancy CRF (Form 14) and SAE/Notable Event CRF (Form 11) should be completed; this should also be discussed directly with the Trial Manager. Please refer to section 7.2 for further information. Follow-up within the trial should continue.

# 5.5 OVERDOSE OF TRIAL TREATMENT

Should an aspirin overdose be suspected, the trial treatment should be withheld and local guidance and pathways should be followed. The MRC CTU at UCL should be informed about all aspirin overdoses and the appropriate adverse event reporting should be followed, see section 7. In the event of overdose, emergency unblinding is available (see section 5.6.1). In the UK, for additional guidance please contact the National Poisons Information Service (www.toxbase.org).

# 5.6 UNBLINDING

Randomisation codes are held within the MRC CTU at UCL randomisation system. Since blinding is critical to the integrity of the study, unblinding a participant's trial treatment during the trial is strongly discouraged unless it is a medical emergency and knowledge of treatment allocation will alter clinical management.

# 5.6.1 EMERGENCY UNBLINDING

Unblinding should generally only be considered in the event of a medical emergency (for example, an emergency operation is required or an overdose has been taken) where knowledge of the participant's treatment allocation would change clinical management.

Unblinding for any purpose other than a medical emergency is generally not allowed, but individual cases should be discussed with the MRC CTU at UCL or TMC/CRO if it is believed to be necessary for the medical care of the participant. Wherever possible, unblinding should be avoided to protect the integrity of the Add-Aspirin trial.

For any treatment code unblinding, the reason for the decision to unblind and the parties involved must be documented in the participant's medical record and on the Unblinding CRF (Form 13). Treatment identification information should be kept confidential and should be disseminated only to those individuals that must be informed for medical management of the participant. Wherever possible, the trial teams involved in the day-to-day running of the projects (MRC CTU at UCL, TMC, CRO) will remain blinded.

# 5.6.1.A UK Unblinding

Where unblinding is being considered during working hours (Mon - Fri, 09:00 - 17:00 UK time), the case should first be discussed with the MRC CTU at UCL by contacting the Add-Aspirin Trial Managers who will contact one of the Trial Physicians. During out of hours, the Investigator (or assigned deputy) should have determined that the information is necessary, i.e. that it will alter the participant's immediate management. When the emergency is clearly not related to the investigational product, the problem may be appropriately managed by assuming that the participant is receiving the highest possible dose of active product (300mg aspirin), without the need for unblinding. Where it is deemed necessary, unblinding can be performed via an access-controlled system available through the trial website (www.addaspirintrial.org).

# 5.6.1.B India Unblinding

: Where unblinding is being considered, the CRO should be contacted in the first instance. The case will normally then be referred to the clinical leads at TMC for advice before unblinding is performed. Full details of this process, including contact details are provided in the Indian group specific appendix.

# 5.6.1.C Republic of Ireland Unblinding

Where unblinding is being considered during working hours (Mon - Fri, 09:00 - 17:00 UK time), the case should first be discussed with the MRC CTU at UCL by contacting the Add-Aspirin Trial Managers who will contact one of the Trial Physicians. During out of hours, the Principal Investigator and other authorised invesitgators are able to access the unblinding system.

The PI or investigator should have determined that the information is necessary, i.e. that it will alter the participant's immediate management. When the emergency is clearly not related to the investigational product, the problem may be appropriately managed by assuming that the participant is receiving the highest possible dose of active product (300mg aspirin), without the need for unblinding. Where it is deemed necessary, unblinding can be performed via an access-controlled system available through the trial website (www.addaspirintrial.org).

For further unblinding information, please refer to the Add-Aspirin Unblinding Procedure For Site – Republic of Ireland.

# **5.6.2** UNBLINDING FOR SAFETY REPORTING

MRC CTU at UCL staff who are not involved in the day-to-day running of the trial will be responsible for unblinding possible suspected unexpected serious adverse reactions (SUSARs) and notable events for notification to the regulatory authorities.

# 5.7 PROTOCOL TREATMENT DISCONTINUATION

In giving consent to participate in the trial, participants are giving consent to have trial treatment, trial follow-up and data collection. However, an individual participant may stop treatment early for any of the following reasons:

- Unacceptable toxicity or adverse event
- Intercurrent illness that prevents further treatment
- Any change in the participant's condition that justifies the discontinuation of treatment in the Investigator's opinion. This might include prescription of aspirin or another medication that the Investigator feels could not safely be given alongside the trial treatment.
- Inadequate compliance with the protocol treatment in the judgement of the Investigator (compliance should be discussed and documented at each follow-up visit as indicated in the assessment schedule)
- Pregnancy
- Early cessation of trial treatment by the participant

As participation in the trial is entirely voluntary, a participant may choose to discontinue the trial treatment at any time without giving any reason, and without their medical care or legal rights being affected. Although the participant is not required to give a reason for discontinuing their trial treatment, any reasons given will be documented on the Early Cessation of Trial Treatment CRF (Form 12).

Participants should remain in the trial for the purpose of follow-up and data analysis unless they additionally wish to withdraw their consent for this. If a participant wishes to withdraw from trial follow-up, refer to section 6.9.

# 5.8 TREATMENT FOLLOWING DISEASE RECURRENCE/PROGRESSION

When disease recurrence has occurred in patients during the randomised phase of the study, participants should normally continue to take their allocated trial treatment. Where the Investigator feels that this is not appropriate (for example, if the participant will be receiving another treatment that cannot safely be given alongside the trial medication), this should be managed and documented as with any other treatment discontinuation (see section 5.7) and the participant should continue to be followed up in the trial wherever possible. See also section 5.11.4 for guidance on managing participants that require non-trial medication. A temporary discontinuation of trial medication could be considered. Unblinding should not normally be required. It is preferable to assume that the participant is taking an active product (300mg aspirin) and discontinue trial medication (either temporarily or permanently) if necessary. Individual cases can be discussed with the MRC CTU at UCL.

If a disease recurrence event happens during the run-in phase, the participant will not be eligible for randomisation and should not be followed up in the trial.

Note that disease recurrence is an important outcome event in all four tumour site-specific cohorts and should be assessed according to protocol definitions (see section 10.2) and documented on the appropriate CRF(s).

## 5.9 ACCOUNTABILITY & UNUSED DRUG

Pharmacies will be provided with trial-specific drug accountability procedures in the Add-Aspirin DSMS user guide and Add-Aspirin Pharmacy Working Instructions.

#### 5.10 ADHERENCE

A high rate of adherence to treatment is required and Investigators are responsible for ensuring that participants understand this. Prior to registration, Investigators and any other trial staff involved in the consent process should ensure that participants fully understand the trial treatment and the importance of adherence, and that over-the-counter aspirin or products containing aspirin must not be taken. This should be re-iterated at face-to-face (or telephone) follow-up visits at the specified time points and adherence should be positively encouraged. Patient-reported adherence should be recorded on follow-up CRFs. Please refer to section 6.2 for guidance on assessing adherence during the run-in period

#### 5.11 NON-TRIAL TREATMENT

#### 5.11.1 MEDICATIONS PERMITTED

All non-contraindicated medications that the responsible clinician feels are appropriate, for example, PPI, paracetamol and remedies for cough and colds, are allowed in the trial. However, the potential for interaction with aspirin of all medicines should be checked against the information provided by the BNF (www.bnf.org) or local equivalent. Information on concomitant medication that has potential anti-cancer activity will be collected at each follow-up visit and call.

#### 5.11.2 MEDICATIONS NOT PERMITTED

Medications not permitted include anti-coagulant and anti-platelet medication, aspirin (including over the counter preparations) and others including methotrexate. See appendix I for a list.

Regular NSAID use is not permitted. NSAIDs should be avoided wherever possible but short-term intermittent/occasional NSAID use is allowed (maximum of 2 consecutive weeks of regular use). Long-term systemic corticosteroids are not permitted but short-term intermittent use is allowed (maximum of two consecutive weeks). See appendix I for further details. Participants should be counselled about over the counter aspirin and NSAID use prior to registration and this should be reinforced at follow-up visits. If longer term use of non-permitted medication is necessary, a treatment break should be initiated. If use is to be longer than 3 months trial treatment should be permanently discontinued. If a patient is found to have been using non-permitted medication concomitantly with trial medication, clinical review of the patient should be performed and MRC CTU should be contacted for advice.

[figure not shown]
#### 5.11.3 MEDICATIONS TO BE USED WITH CAUTION

Aspirin has the potential to interact with the following medications and should therefore be taken with caution: selective serotonin reuptake inhibitors (SSRIs), Iloprost, kaolin, metoclopramide, phenytoin, probenecid, spironolactone, sulfinpyraxone, thiopental, valproate, venlafaxine and zafirlukast. See the BNF for further details and a full list of interactions.

#### 5.11.4 MANAGEMENT WHERE A MEDICATION THAT IS NOT PERMITTED BECOMES INDICATED DURING THE TRIAL

We would not expect patients who require a medication that is not permitted in the trial (see appendix I) to be registered for Add-Aspirin because this should have been identified previously. However there may be participants who develop a medical condition during the trial where a medication that is not permitted becomes clinically indicated. Examples include but are not limited to: anti-coagulation for the treatment of pulmonary embolism, deep vein thrombosis or atrial fibrillation and anti-platelet therapy for the management of cardiovascular events.

For management where a medication that is not permitted becomes indicated see the flow diagram (figure 3) and corresponding notes.

# Figure 3. Management where a medication that is not permitted becomes indicated

These notes refer to the points on the flow diagram in figure 3.

- a. Where a medication that is not permitted is thought to be clinically essential the investigator should liaise with the relevant specialist (e.g. a cardiologist) to make this decision. Advice on individual cases will also be available from the Add-Aspirin trial management group which includes cardiovascular experts.
- b. In an emergency situation the trial treatment should be immediately withheld and the non-permitted medication started. This should be reviewed with the relevant specialist advice at the first available opportunity. Unblinding should be avoided if possible.
- c. Emergency unblinding is available but should only be performed where knowledge of the trial treatment would alter immediate clinical management (see section 5.6.1).

- d. Where the trial treatment is withheld or expected to be withheld for more than 3 months the trial treatment should be permanently discontinued. The participant should continue to be followed up in the trial. Participants in the run-in period will be asked for consent to allow passive follow-up data collection using medical records.
- e. The trial treatment can be restarted when all medications that are not permitted have been discontinued, provided it has been withheld for less than 3 months (if greater than 3 months, individual cases can be discussed with MRC CTU at UCL).

Prescribing aspirin for its analgesic, anti-pyrexic or anti-inflammatory actions to provide symptomatic relief (e.g. headache, toothache, migraine, neuralgia, sore throat and dysmenorrhoea) should be avoided and alternative medications (e.g. paracetamol) should be considered.

MRC CTU at UCL should be informed of any event where a medication that is not permitted becomes indicated. If applicable the appropriate SAE and Notable Event CRF (Form 11) should be completed within 24 hours of the Investigator becoming aware of the event (see section 7).

# 6 ASSESSMENTS & FOLLOW-UP

#### 6.1 TRIAL ASSESSMENT SCHEDULE

The frequency of follow-up visits and assessments are detailed in the Trial Assessment Schedule (see page xi - xiv). As far as possible, trial follow-up visits and assessments have been aligned with standard practice.

# 6.2 PROCEDURES FOR ASSESSING SUITABILITY FOR RANDOMISATION FOLLOWING THE RUN-IN PERIOD

Assessments at the end of the run-in period will focus on treatment adherence and toxicity in order to determine the participant's suitability for randomisation into the trial. Participants will be provided with a diary card to complete during the run-in treatment period. They will be asked to bring this, along with their used blister packs, to their subsequent visit and these will be used to assess adherence. Toxicity will be assessed and documented using CTCAE v4 as for all other follow-up visits. Other assessments at this time include a blood test, blood pressure and an update on usage of concomitant medications, all of which will be assessed as described in section 6.4 for other follow-up visits.

The run-in period should be 7-9 weeks long. Participants will be suitable for randomisation if they have taken at least 80% of their run-in treatment (6 or 7 tablets per week) and have not experienced any aspirin-related severe toxicity (defined as ≥grade 3 CTCAE v4), nor significant gastrointestinal bleeding (grade 3 or 4), active gastrointestinal ulceration, new cases or worsening tinnitus (grade 2 or above), intracranial bleeding or hypersensitivity to aspirin. The Investigator is responsible for the final decision as to whether participants are suitable to be randomised but the Trial Management Group will be available for discussion via the Trial Manager if there are concerns or uncertainties.

The run-in period can be extended where the Investigator decides there is a valid reason for inadequate adherence (e.g. unforeseen social circumstances), or the cause of inadequate adherence is temporary (e.g. reversible dyspepsia, see section 5.4.3.A). Additionally this may apply to patients who may be eligible for CAPP3 and are awaiting results of genetic testing. Where offered, the run-in period would normally be extended by 4 or 8 weeks after which adherence and toxicity would be reassessed in the same way. All extensions to the run-in period must be pre-approved by MRC CTU at UCL via the Trial Managers and only one extension for a maximum of 8 weeks is permitted per participant.

# 6.3 PROCEDURES FOR ASSESSING EFFICACY

Clinical outcome events, as defined in the Statistical Analysis Plan, will be reported on CRFs to be completed by the Investigator or Research Nurse at each follow-up assessment. Disease recurrence and progression will be assessed at follow-up clinic visits by means of imaging, clinical examination and tumour markers (e.g. carcinoembryonic antigen (CEA), prostate-specific antigen (PSA)) in accordance with routine investigations for that tumour site (see Trial Assessment Schedule). In the prostate cohort, biochemical failure is a primary outcome event and should be reported in accordance with the definitions provided in 6.3.1.

Following disease recurrence/progression in the randomisation phase, participants should normally continue to take their trial medication (see section 5.8 for guidance on treatment following

relapse/progression). Providing they are willing, they should continue to be followed up in the trial, regardless of whether they are still receiving trial medication. Follow-up should adhere as far as possible to the planned assessment schedule, but some variation is acceptable where this differs from local protocols for follow-up after relapse.

# 6.3.1 DEFINITIONS OF BIOCHEMICAL FAILURE EVENTS IN THE PROSTATE COHORT

In the prostate cohort, biochemical (PSA) failure is a primary outcome event and is defined as follows, according to primary treatment pathway:

- **Participants who have undergone prostatectomy:** failure occurs in the case of a PSA value greater than 0.2ng/ml, observed at least 6 weeks after surgery, which is confirmed by a subsequent PSA value higher than the firsta.
- **Participants who have undergone radical radiotherapy:** the failure value is defined as nadir+2ng/mlb, with failure occurring in the case of a PSA value exceeding the failure value which is confirmed by a subsequent PSA value higher than the firsta.
- Participants who have undergone salvage radiotherapy (following a rise in PSA after prostatectomy): failure occurs in the case of:
  - (i) a PSA value greater than 0.1ng/ml which is confirmed by a subsequent PSA value higher than the firsta; or
  - (ii) three consecutive rising PSA values

Notes on the definitions:

- a) In all cases the confirmation PSA test should be performed between 1 week and 3 months after the initial failure. The event will be reported as having occurred on the date of the original (first) test with the corresponding PSA value.
- b) The PSA nadir will be the lowest reported PSA value between registration and (up to and including) the 6-month follow-up visit.

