## Flexibility of Schedules and Follow Up:

To allow for variations in standard practice across sites, the following are permitted:

- Consent can be taken by research nurses, where delegated by the local Principal Investigator (PI), in the UK only.
- Follow-up can be led by a nurse member of the research team provided:
  - Appropriate clinical support is available
  - In the event of any adverse events, toxicities or other concerns, the participant will be seen by a doctor
- Follow-up at each time point should be conducted +/- 2 weeks from the date of randomisation wherever practically possible.
- Cognitive assessments (UK and Republic of Ireland only):
  - Can be performed over the telephone where no visit is planned
  - Can be administered by a non-clinical staff member (e.g. Data Manager)
- Routine imaging examinations and blood tests should be used when performed within in the specified timelines (see below) where available. Imaging examinations and blood tests do not need to be trial specific.
- Imaging examinations can be performed within +/-6 months from scheduled assessment point. Additional imaging examinations should be performed if clinically indicated.
- Where a visit is additional to local standard care, assessments can be conducted over the phone provided:
  - The protocol schedule is followed, including blood tests
  - Appropriate measures for dispensing trial medications are made
- Weight should be assessed as part of clinic visits but can be omitted where telephone follow-up is planned (as above).
- Blood pressure checks must be performed at the registration and end of run-in visit, and thereafter should be performed at least annually whilst patients are on trial treatment. These assessments would normally be performed as part of clinic visits, but can be collected via the GP or home readings where telephone follow-up is planned.
- Breast cohort only: No imaging is needed in the case of bilateral mastectomy. Alternative follow-up imaging (such as MRI in younger patients) is acceptable in place of mammography..
- Colorectal cohort only: it is expected that at least two of the three scheduled surveillance colonoscopies are performed, provided that the whole colorectum is visualised in the perisurgical period. The 5 year colonoscopy is mandatory.
- Colorectal cohort only (UK centres): If participant is also enrolled in POLEM, follow trial assessment schedules found in Appendix XIV (Section 5).

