## **PROSTATE COHORT**

					М	ONTHS	SINCE	RANDO	MISAT	ION (E)	KCEPT	WHERI	E INDIO	CATED)		
		CRF NUMBER	PRIOR TO REGISTRATION	PRIOR TO RANDOMISATION (END OF RUN-IN PERIOD)	3	6	9	12	18	24	30	36	42	48	54	60
Main	Registration assessments 	1pc, 3, 4, 16*	✓													
Main	End of run-in assessment 	7		✓												
assessments	Follow-up assessments 	8, 8pc			✓	✓	✓	✓	✓	✓	✓	✓	✓	✓	✓	✓
	VES-13 questionnaire  (65≥ years at registration)	5	~													~
Intermittent	Cognitive assessment 	6	✓					✓								✓
assessments	International Physical Activity Questionnaire	8						~								-
	PSA	1рс, 7, 8рс	✓	✓	✓	✓	✓	
 
✓
 
	
 
✓
 
	✓	✓	✓	✓	✓	✓	✓
Disadasta	FBC, LFT, U&E & eGFR	3, 7, 8	✓	✓		✓		✓		✓		✓		✓		✓
Blood tests	C-Reactive Protein (CRP)	3, 8	✓			✓		✓								
	Fasting lipid profile	3	✓													
Other tests	Tumour and blood sample to be stored in bio-bank 	2	~													
	Urine sample to be stored in bio-bank 	2a	✓	✓	1											
	(selected centres only)															

 Registration assessments include: eligibility, co-enrolment (\*if applicable), blood pressure, height, weight, blood results, concomitant medication and comorbidities.

 End of run-in assessments include: symptoms and toxicity, adherence, blood pressure.

 Follow-up assessments include: symptoms and toxicity, adherence, blood pressure, weight, concomitant medication.

 UK and RoI only

 Where participants have given their consent.

 **Rol:** samples processed and stored locally at sites. **India:** Tumour blocks will be collected at all sites and sent for storage at TMC; blood sample collection is only applicable at TMC.

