# 4.2.4 PROSTATE COHORT

For these participants, hormone therapy may be planned or ongoing (for a maximum duration of 3 years). A diagram of the timing of entry criteria for the prostate cohort is available in appendix XI.

- a) **Prostatectomy and no adjuvant chemotherapy or radiotherapy planned:** the run-in period should start between 6 and 12 weeks after definitive surgery, providing PSA remains ≤0.1 ng/ml at point of entry. **India only:** the run-in period should start between 2 and 12 weeks after definitive surgery and where registration is before 6 weeks PSA ≤0.1ng/ml should be confirmed at the time of randomisation.
- b) **Prostatectomy and adjuvant radiotherapy:** the run-in period should start at least 6 weeks after surgery and no later than 6 weeks after the last fraction of radiotherapy.

- c) **Radical radiotherapy:** the run-in period can start as soon as this is complete and no later than 12 weeks after the final fraction of radiotherapy.
- d) Salvage radiotherapy following previous prostatectomy (irrespective of previous therapy): the run-in period should start no later than 12 weeks after the final fraction of radiotherapy.

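### After radical radiotherapy the PSA nadir is closed at the 6-month visit, so in men whose PSA is still falling the failure value is set too high and PSA failure can be dated late or missed by month 60

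*Protocol*

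**What the plan says.** In the prostate cohort, PSA failure as defined in Protocol section 6.3.1 is one component of the primary outcome, bRFS (section 10.2.1, Table 7). The other components are clinical progression, start of salvage treatment and prostate cancer death.

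For men treated with radical radiotherapy, "the failure value is defined as nadir+2ng/ml", and a value above it counts once a subsequent, higher PSA confirms it. Note (b) fixes the nadir: "The PSA nadir will be the lowest reported PSA value between registration and (up to and including) the 6-month follow-up visit". Note (a) requires the confirmatory test between 1 week and 3 months after the first. The prostatectomy and salvage radiotherapy definitions do not use a nadir, so the point concerns the radical radiotherapy group only.

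The timing of the 6-month visit relative to treatment follows from three places:

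- Section 4.2.4: "the run-in period can start as soon as this is complete and no later than 12 weeks after the final fraction of radiotherapy".
- Section 6.2: "The run-in period should be 7-9 weeks long", and "only one extension for a maximum of 8 weeks is permitted per participant".
- Flexibility of Schedules and Follow Up: "Follow-up at each time point should be conducted +/- 2 weeks from the date of randomisation wherever practically possible".

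The prostate assessment schedule has PSA at registration, at the end of run-in, and at every follow-up visit to month 60: 3-monthly to month 12, then 6-monthly. Section 4.2.4 allows hormone therapy for up to 3 years. It is permitted, not required. No section lets the nadir be updated after month 6 or gives a reason for the limit.

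**The concern.** A nadir-plus-constant rule measures a rise from the man's own lowest value. If the window closes while his PSA is still falling, the reference is not his lowest value and the failure value is too high. A man with PSA 2.0 ng/ml at month 6 and 0.5 ng/ml at month 18 keeps a failure value of 4.0, although he has risen by 2 ng/ml once he passes 2.5.

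Men already suppressed by hormone therapy at month 6 are little affected. The same rule is therefore laxer for some men than for others, according to co-treatment.

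At stake is the event count and event timing in a group that section 10.4.4 powers separately. Scheduled PSA ends at month 60, so a crossing pushed past that visit may not be recorded as a PSA failure.

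**Working it through.** **1. When the nadir window closes, counted from the last fraction.** Add the time to run-in start, the run-in and 26 weeks; one month is 4.35 weeks.

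- Earliest: 0 + 7 + 26 = 33 weeks = 7.6 months.
- Latest: 12 + 9 + 26 = 47 weeks = 10.8 months.
- With the 2-week visit window: 31 to 49 weeks = 7.1 to 11.3 months.
- Latest with an 8-week run-in extension: 47 + 8 = 55 weeks = 12.6 months.

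**2. Direction.** A running nadir (lowest value to date) can never exceed the lowest value up to month 6. The failure value under note (b) is therefore equal or higher, and failure is dated the same or later, never earlier. This needs no assumption.

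**3. Size of the delay in assumed PSA courses.** The protocol gives no PSA kinetics, so these inputs are assumptions: PSA at month 6 of 0.5, 1 or 2 ng/ml; further fall with a 6-month half-life to a nadir at month 12, 18 or 24; then exponential rise with a doubling time of 6 or 12 months. That makes 18 courses.

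Delay = doubling time × log2[(month-6 PSA + 2) / (true nadir + 2)].

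- Smallest: 6 × log2(2.5/2.25) = 0.9 months.
- The man in the example, doubling time 12 months: 12 × log2(4.0/2.5) = 8.1 months.
- Largest: 12 × log2(4.0/2.25) = 10.0 months.

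The failure value is 2.5 to 4.0 ng/ml with the fixed nadir, against 2.06 to 3.0 with the running nadir.

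**4. The same 18 courses on the protocol's visits to month 60.**

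| Recorded PSA failure, fixed v running nadir | Courses |
|---|---|
| Same visit | 7 |
| 6 months later | 5 |
| 12 months later | 1 |
| Missed by month 60 | 1 |
| No failure by month 60 under either rule | 4 |

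Five of the six later-dated courses sit on a tie: PSA equals 4.0 exactly at a visit, which does not exceed the failure value. If each tie counts as a failure, the split becomes 11 same visit, 2 later by 6 months, 1 missed and 4 neither. Of the 14 courses that fail under the running nadir, 7 to 11 thus keep their date. The missed course has PSA 1.0 at month 6, nadir 0.25 at month 18 and doubling time 12 months. It crosses the running value at 18 + 12 × log2(2.25/0.25) = 56.0 months and the fixed value at 18 + 12 × log2(3.0/0.25) = 61.0 months.

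**5. What lost events would cost.** First the plan's own figure. Section 10.4.4 asks for 443 events (173 control) for HR 0.73, 90% power, two-sided 5%. Freedman's formula with 2:1 allocation gives (1.960 + 1.282)² × (1 + 2 × 0.73)² / [2 × (1 − 0.73)²] = 436, within 3% of 443. Power is then Φ{√(2d) × 0.27/2.46 − 1.96}:

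| Share of events lost (assumed) | Events d | Power |
|---|---|---|
| 0% | 443 | 90.4% |
| 5% | 421 | 89.0% |
| 10% | 399 | 87.3% |
| 20% | 354 | 83.2% |

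This applies only if the calendar date of analysis is fixed. Section 10.4 ties timing to control-arm events, so late events would otherwise delay the analysis.

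**The case against.** The strongest reply is that section 6.3.1 is clear, prespecified and contradicted nowhere, and that the case rests on men still falling at 8 to 11 months, a share the protocol does not give. That stands as a limit on size. It does not touch the direction, or the fact that collected values go unused.

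Three stronger readings are tempting and are not supported.

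- *Failures in this group are dated late or missed as a rule.* Men whose lowest PSA falls by month 6 are unaffected, and most or about half of the assumed failing courses keep the same visit date.
- *The treatment comparison is biased.* The rule is identical in every arm of a double-blind trial, and section 10.8.1 adjusts for prognostic factors. Nothing in the protocol shows a bias in the hazard ratio.
- *Missed PSA failures are lost to bRFS.* Progression, salvage treatment and prostate cancer death recapture some. Active follow-up lasts at least 5 years, and UK routine data then supply recurrence details, though the sources listed in section 9.3.1 do not include PSA values.

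A running nadir also has costs. Small transient rises reach nadir + 2 more often; the confirmatory test limits this. Failures re-derived from past data will often lack that test in the 1-week to 3-month window, because visits are 6-monthly after month 12 and the site had no reason to repeat the PSA. This stands, and the change must deal with it. The statistical analysis plan, not seen here, may already hold a running-nadir sensitivity analysis, but the primary definition is the one in the protocol.

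**Conclusion.** The point holds as a weakness in a primary-outcome definition. Note (b) closes the nadir 7.6 to 10.8 months after the last fraction on the standard timetable. For a man still falling then, the failure value is too high and PSA failure can be dated later than it should be, or missed by month 60.

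The direction is certain; the size is not known. In the assumed courses the crossing moves by 0.9 to 10 months, and of 14 failing courses 2 to 6 are recorded later and 1 is missed. The effect is larger when PSA at month 6 is higher and the rise is slower. The share of men affected, mainly those not suppressed by hormone therapy, would have to come from the trial's own data.

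The consequence is later, less precise or fewer bRFS events in the radiotherapy group: a delayed analysis or, at a fixed date, a modest loss of power. The event target of 443 is not in dispute.

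**What to change.** Change note (b) of section 6.3.1 so that the nadir is the lowest PSA reported from registration up to the test being assessed. Apply it prospectively, with a note to sites, so that the note (a) confirmatory test is obtained at the lower failure value.

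For PSA values already recorded, state in advance how a crossing without a confirmatory test in the 1-week to 3-month window is handled; for example, accept the next scheduled PSA if it is higher. Report the fixed 6-month nadir as a sensitivity analysis. If the 6-month limit was deliberate, give the reason and reverse the roles of the two definitions.

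Cost: one line of text, a programmed derivation and a site note. No visits or scheduled PSA tests are added; confirmatory tests would be triggered at a lower value in some men. The failure value then changes over time, so the CRF check must compute it, and transient rises may more often reach nadir + 2.
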